5.3 Analysis Sets

The **Enrolled Set** includes all subjects with confirmation of eligibility at Screening.

The **Screening Failure Set** (SFS) consists of all subjects who started screening but didn't receive IMM-101 for whatever reason. The SFS will include subjects who were eligible at Screening but no longer eligible at Visit 1.

The **Intent-to-Treat (ITT) Set** includes all subjects receiving at least one dose of IMM-101, irrespective of compliance with eligibility and other protocol criteria.

The **Per-Protocol Set** (PPS) is a subset of the ITT Set with no major protocol deviations. Major protocol deviations are described in more detail in Section 5.6. The PPS will include both Cohort A and Cohort B patients, although any outputs presented on the PPS will summarise Cohort A only.

The **Safety Analysis Set** (SAF) includes all subjects receiving at least one dose of IMM-101, irrespective of compliance with eligibility and other protocol criteria.

The list of subjects included in the analysis sets will be agreed prior to database lock, once all study data is available. The membership of the ITT and SAF analysis sets is anticipated to be the same.

5.4 Data Presentations

The data will be summarised in tabular form by Cohort apart from disposition of subjects, protocol deviations, background and demographic data (including baseline disease status, medical history, previous melanoma treatment and surgery,

prior/concomitant medications and concomitant surgeries), exposure, compliance and adverse events which will be summarised by Cohort and overall subjects. Cohorts will be labelled 'Cohort A' and 'Cohort B'.

Listings will be sorted by Cohort, subject number and date/time of assessment. Where listings are presented for all subjects, any screening failure subjects will be presented separately from enrolled subjects.

Data will be summarised and listed using the analysis sets as defined in Table 1 of this SAP.

Table 1: Analysis sets used to present summaries and listings

	All Subjects	Enrolled	ITT	SAF
Tables	
 Disposition 		
 Protocol deviations Demography Baseline disease status Compliance Efficacy (repeated on PPS for selected outputs for Cohort A only) 	
 Medical history Previous melanoma treatment/radiotherapy/surgery Prior and concomitant medications Concomitant surgical procedures Exposure Adverse events Injection site reactions Clinical laboratory parameters Vital signs
Listings	
 Completion/withdrawal Eligibility Protocol deviations Analysis sets Informed consent Demography Melanoma diagnosis Visit dates 	
 Time on study and study drug exposure Medical history Previous melanoma treatment/radiotherapy/surgery Prior and concomitant medications Concomitant surgical procedures Baseline, follow-up and new lesions Response assessment Serology sample Pregnancy test PD-L1 biopsy BRAF testing Blood and biopsy samples Vital signs ECG results Physical examination ECOG performance status 	
 Efficacy 	
 Post completion anti-melanoma treatment Administration Adverse events Injection site reactions Clinical laboratory parameters

For safety summaries, only scheduled post-baseline data will be tabulated, post-baseline repeat/unscheduled assessments will be disregarded, although they will be listed and in particular all clinically significant values will be noted.

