#### 9.4 LABORATORY EVALUATION

Clinical laboratory evaluations will be assessed (prior to administration of IMM-101) using the parameters and timelines presented in **Table 1**.

Abnormal laboratory test results considered to be clinically significant will be recorded as an AE in the patient's eCRF and the patient will be followed-up until the laboratory value has returned to normal range or stabilised at a non-clinically significant value.

Any additional blood tests to those scheduled in this study will be performed as per the Investigator's routine procedures.

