### 11.1.4 Other Safety Endpoints

# Safety Laboratory Parameters

Laboratory parameter results will be summarised descriptively for continuous parameters, by assessment time point using summary statistics of actual values and change from baseline values. In addition, 'shift' tables of the number and percentage of patients with values outside normal range and within normal range at post baseline assessments by baseline assessment will be presented. Abnormal values will be flagged in data listings.

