2.2.2 Secondary Endpoints

The secondary efficacy endpoints of the study are:

- PFS assessed by RECIST 1.1 after a maximum of 18 months treatment in patients receiving IMM-101 + nivolumab.
- OS and OS at 1 year, for both cohort A and cohort B. The median OS (if applicable) and OS rate at 12 months will be estimated.

The secondary safety endpoints of the study are:

- Incidence and frequency of laboratory parameter abnormalities.
- Change from baseline values in laboratory parameter values.
- Incidence and frequency of local injection site reactions.

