5.15.3 Clinical Laboratory Evaluation

Observed values and change from baseline in haematology and biochemistry assessments will be summarised over time. If the test results are reported in categorical format, the results will be summarised by subject counts and percentage for each category.

Each haematology and biochemistry parameter will be classed as low, normal, high or missing based on the reference ranges. Shift tables in relation to the reference range from baseline over time will be presented.

Tables summarising clinical significance over time for haematology and biochemistry will also be presented.

Haematology and biochemistry data will be listed separately including change from baseline, reference ranges flagging all out of range values and their clinical significance.

Dipstick urinalysis and serology data will be listed only.

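### The SAP text plans no patient-level, any-time table of laboratory abnormalities, and values seen only at unscheduled draws are left out of the laboratory tables

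*SAP*

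**What the plan says.** SAP 2.2.2 names "Incidence and frequency of laboratory parameter abnormalities" as a secondary safety endpoint. Protocol 5.2.2 and 11.1.3 carry the same endpoint, with no restriction to scheduled visits.

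SAP 5.4 sets the rule for all safety summaries: "only scheduled post-baseline data will be tabulated, post-baseline repeat/unscheduled assessments will be disregarded". The sentence goes on: "although they will be listed and in particular all clinically significant values will be noted".

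SAP 5.15.3 then describes the laboratory output:

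- observed values and changes from baseline, over time;
- "Shift tables in relation to the reference range from baseline over time will be presented";
- a tabulation, again by time point, of which haematology and biochemistry results were judged clinically significant;
- listings that include "reference ranges flagging all out of range values and their clinical significance".

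Protocol 11.1.4 describes shift tables of patients "with values outside normal range and within normal range at post baseline assessments by baseline assessment will be presented" and does not limit them to scheduled assessments. SAP section 6, which lists changes from the protocol analysis, does not mention the scheduled-only rule.

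Outside the laboratory tables, protocol 9.4 states: "Abnormal laboratory test results considered to be clinically significant will be recorded as an AE in" the patient's eCRF. It makes no distinction between scheduled and unscheduled tests.

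**The concern.** An incidence of laboratory abnormalities is naturally read as the proportion of patients with at least one abnormal value on study. Tables by time point do not give it. The same patient can appear at several visits, so the columns cannot be added up to a number of patients. Under SAP 5.1, laboratory percentages also rest on non-missing observations, so the denominator changes from visit to visit.

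The scheduled-only rule then removes values from those tables. Leaving values out can lower an any-time count or leave it unchanged; it can never raise it. The SAP avoids this elsewhere: in 5.2.4 all scans count for efficacy, scheduled or not, and in 5.15.2 injection site reactions are summarised at the worst grade per patient over the whole study. Laboratory abnormalities, also a secondary safety endpoint, get neither treatment.

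At stake is a small understatement of laboratory toxicity for a new combination, in a study where safety is one of the two primary objectives.

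**Working it through.** The documents state no figure on this point, so there is none to reproduce. The check is a comparison of passages, followed by arithmetic on size.

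**1. Where an abnormal value at an unscheduled post-baseline draw ends up**

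| Output | Included? |
|---|---|
| Summaries and shifts over time (SAP 5.15.3) | No, by the SAP 5.4 rule |
| Clinical significance over time (SAP 5.15.3) | No, same rule |
| Laboratory listings (SAP 5.15.3) | Yes, flagged if out of range |
| TEAE tables by SOC and PT (SAP 5.15.1) | Only if recorded as an adverse event |

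Baseline is not affected: SAP 5.2.1 takes the last value before the first IMM-101 dose, and the SAP 5.4 rule concerns post-baseline data.

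**2. Can such values arise?** Protocol 9.4 allows additional blood tests under the investigator's routine procedures. In protocol 8.2 the nivolumab-only visits (Weeks 6, 14, 18, 22 and so on) list no safety bloods, and the additional ipilimumab schedule in Appendix 1 lists none. Any bloods taken at those visits would be unscheduled.

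**3. Would scheduled draws pick up the same abnormality?** Protocol Table 1 gives draws at Weeks 2, 4, 8, 10, 12 and then every 4 weeks to Week 76. Starting from Week 0 and placing the end-of-study draw at Week 80 gives 4 gaps of 14 days and 18 gaps of 28 days: 4 × 14 + 18 × 28 = 560 days. Assume onset is uniform over these 560 days and the abnormality lasts *d* days. The chance that it falls wholly between two scheduled draws is the sum of max(0, gap − *d*) over all gaps, divided by 560:

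- *d* = 7: (4 × 7 + 18 × 21)/560 = 406/560 = 72.5%
- *d* = 14: (18 × 14)/560 = 252/560 = 45.0%
- *d* = 21: (18 × 7)/560 = 126/560 = 22.5%
- *d* = 28: 0%

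The durations are assumptions, shown as a range. Short-lived abnormalities can be missed at scheduled draws; those lasting 28 days or more are not, if the schedule is kept.

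**4. Size per patient.** With the planned cohort sizes as denominators, one patient whose only abnormality is unscheduled adds 1/18 = 5.6 percentage points in Cohort A and 1/8 = 12.5 in Cohort B.

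For scale, the exact (Clopper-Pearson) 95% intervals for 0 and for 1 patient are:

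| | 0 patients | 1 patient |
|---|---|---|
| Cohort A (n = 18) | 0 to 18.5% | 0.1 to 27.3% |
| Cohort B (n = 8) | 0 to 36.9% | 0.3 to 52.7% |

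The SAP plans no intervals for laboratory data; these only show how much one patient matters.

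**The case against.** The strongest reply is that the values are not lost. They are listed, out-of-range results are flagged, and clinically significant ones are noted. Clinically significant results must be recorded as adverse events, and those tables are by SOC and PT, not by visit, with separate counts for serious, immune-related and Grade 3 or above events. An abnormality in a patient who is unwell is the kind most likely to reach them. This stands. A reader might infer from SAP 5.4 that abnormalities found between visits are counted nowhere; the documents do not support that.

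A reader might also conclude that the endpoint is not analysed at all. That too goes too far. Shift and clinical-significance tables are planned, protocol 11.1.4 plans similar output, and neither document defines the endpoint as the worst value per patient. The table shells are a separate document not available here, so the gap can be stated only for the SAP text.

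Nor do the documents say that extra bloods are taken because toxicity is suspected. They refer only to routine procedures, and the rule also covers repeats. Dosing delays for laboratory abnormalities (protocol 7.2.1) and the resolution required before dosing resumes (7.2.2) make repeats in affected patients plausible, but that is inference.

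Finally, this is a descriptive study of 26 planned patients with full listings and six-monthly safety review. Withdrawing patients should, where possible, have end-of-study bloods. This limits the importance of the point but does not remove it. A listing is not an incidence, and entry as an adverse event depends on an open-label clinical judgement and belongs to a different endpoint. Out-of-range unscheduled values not judged clinically significant and not recorded as adverse events appear in no table.

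**Conclusion.** The point holds as a reporting gap of modest size. As the SAP text stands, the secondary laboratory endpoint has no patient-level any-time table, and abnormalities seen only at post-baseline repeat or unscheduled draws are absent from the laboratory tables. The scheduled-only rule is narrower than protocol 11.1.4 and is not declared in SAP section 6.

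The direction is known: omission can only lower an any-time count or leave it unchanged. The amount is not, because the documents give neither the number of unscheduled draws nor the reasons for them. It would be tempting to say that the reported incidence could be halved, but no figure in the documents supports any particular shortfall. What can be said is 5.6 points per affected patient in Cohort A and 12.5 in Cohort B, assuming full planned enrolment and the whole cohort as denominator. The miss probabilities further assume uniform onset, the nominal draw dates and the durations shown.

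**What to change.** - In SAP 5.15.3, add a table for each haematology and biochemistry parameter using all post-baseline values, scheduled and unscheduled. It should give the number and percentage of patients with any low value and with any high value, and the shift from baseline to worst post-baseline value, by cohort. State the denominator.
- Keep the by-visit tables on scheduled data. For those tables the SAP 5.4 rule is reasonable; amend it so that it does not apply to the new tables.
- List the scheduled-only rule in SAP section 6 as a change from protocol 11.1.4, with a reason.

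The cost is a few extra tables and their shells. No new data collection is needed, since the unscheduled values are already to be listed. Reported rates may look slightly higher than in the by-visit tables.

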5.5 Disposition of subjects

The number and percentage of all subjects enrolled, included in the SFS, ITT/SAF sets and PPS, who completed the study and prematurely discontinued the study, will be summarised. The number and percentage of subjects will be summarised by their reasons for withdrawal from the study.

Eligibility for each of the analysis sets along with reasons for exclusion will be listed. Study completion/withdrawal data will be listed.

5.6 Protocol Deviations

Prior to database lock, the Immodulon Medical Monitor will review all individual deviations and classify them as major or minor during a data review meeting. Decisions arising from the data review meeting will be documented in the minutes and will be approved by the Immodulon Medical Monitor (on behalf of Immodulon) and the Project Statistician. Major deviations considered having a serious impact on the efficacy results will lead to the relevant subject being excluded from the PPS.

Major protocol deviations may include but are not limited to:

- Prior treatment for naïve disease (Cohort A only).
- Active brain metastases or leptomeningeal metastases (Cohort A only).
- Subject enrolled under Protocol Version 1.0 did not receive the minimum 4 doses of anti-PD-1 therapy before progression (RECIST 1.1) was documented and/or more than 8 weeks had elapsed between the last dose of anti-PD-1 therapy and the start of Screening (Cohort B only).
- Subject enrolled under Protocol Version 2.0 did not receive the minimum 3 doses of anti-PD-1 given as a monotherapy or the minimum 2 doses of anti-PD-1 given in combination regimes before progression (RECIST 1.1) was documented and/or more than 12 weeks but less than 6 weeks had elapsed between the last dose of anti-PD-1 therapy and the start of IMM-101 administration (Cohort B only).
- Subject has not received at least one dose of both IMM-101 and nivolumab.
- Subject does not have at least 1 measurable lesion by CT/MRI (RECIST 1.1) at baseline assessment and/or at least one post baseline measurable scan (whether or not scheduled).
- Subject has received on-study prohibited medications considered likely to have had an impact on the efficacy of study medication.

Protocol deviations which can be attributed to the COVID-19 pandemic will be entered into the eCRF with a comment indicating that the deviation is due to COVID-19. No specific COVID-19 category has been added to the eCRF as COVID-19 is a reason for a deviation and not a deviation in itself. However, these COVID-19-related deviations may be summarised under a separate category of COVID-19 if sufficient in

number and in addition to being identified in data listings, as determined at the data review meeting.

Protocol deviations other than those specified above may be identified. Details of all protocol deviations (start and end dates, review and decision date, deviation category, specific details and classification of major or minor) and subject eligibility will be listed.

Protocol deviations, both major and minor, will be summarised for each deviation category.

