#### 11.7 PATIENT SELECTION FOR ANALYSES

# 11.7.1 Analysis Sets

The efficacy and tolerability endpoints will be evaluated using the Intent-to-treat (ITT) set, defined as all patients receiving at least one dose of IMM-101, irrespective of compliance with eligibility and other protocol criteria. This set will also define the Safety set.

In addition, a Per-protocol (PP) set, defined as ITT patients with no major protocol deviations and having complied with the treatment regimens of the combination therapy, will be used to evaluate further the efficacy of the combination therapy for the primary and secondary efficacy parameters.

The data for any enrolled patients who are not in the ITT set (i.e., who do not receive at least one dose of IMM-101) will be listed only.

Page 81 of 98

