6 CHANGES FROM THE PROTOCOL PLANNED ANALYSIS

1. The Cohort A interim data review will be conducted when the first 11 Cohort A subjects enrolled into the study have had the opportunity for 1 year on study. The Cohort B interim data review will be conducted when the first 5 Cohort B subjects enrolled into the study have had the opportunity for 6 months on study. Any further enrolled Cohort A/B subjects will not be included in the data reviews of efficacy, but their AE data will be included in the data reviews of safety.
2. The data cut-off for the interim data reviews has been clarified. This specifies the scan assessments included for each interim data review are derived using dates for each subject and not the nominal scan assessments.
3. Clarification has been made to the definition of the PPS. The definition requires subjects to have complied with the treatment regimen, but this is naturally implied by the definition given any non-compliance would be a protocol deviation.
4. Tables will be produced for the PP analysis set in addition to the ITT analysis set for Cohort A only. Due to the small size of Cohort B, there will be no separate set of tabulations for the PP set in Cohort B. Analysis set assignment and protocol deviations will still be listed for all subjects.

5. Clarification has been made to the requirement for subgroups to be summarised provided the respective subgroup size is at least 33% but less than the total size of the ITT set for Cohort A, and at least 50% but less than the total size of the ITT set for Cohort B.

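### SAP 5.3 and 5.6 give different rules for exclusion from the Per-Protocol Set, and nothing keeps response data out of the review that applies them

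*SAP*

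**What the plan says.** SAP 5.3 states that the PPS "is a subset of the ITT Set with no major protocol deviations" and refers to SAP 5.6 for more detail on what counts as major. Protocol 11.7.1 describes the set as "defined as ITT patients with no major protocol deviations and having complied with the treatment regimens of the combination therapy". Neither text asks how much a major deviation affects efficacy.

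SAP 5.6 describes the process. Before database lock, "the Immodulon Medical Monitor will review all individual deviations and classify them as major or minor during a data review meeting". The resulting decisions are minuted and "will be approved by the Immodulon Medical Monitor (on behalf of Immodulon) and the Project Statistician". It then states: "Major deviations considered having a serious impact on the efficacy results will lead to the relevant subject being excluded from the PPS". The list of examples is open: "Major protocol deviations may include but are not limited to".

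On timing, SAP 5.3 adds: "The list of subjects included in the analysis sets will be agreed prior to database lock, once all study data is available".

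SAP section 6, item 3, records one clarification of the PPS definition, about compliance: "The definition requires subjects to have complied with the treatment regimen, but this is naturally implied by the definition". It mentions no filter on efficacy impact.

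**The concern.** There are two linked problems.

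The first is that the rule is not unique. Two people building the PPS from the same minutes could obtain different sets, depending on whether they follow 5.3 or 5.6.

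The second is that the extra condition in 5.6 is a judgement about effect on efficacy, made late in an open-label trial. In a blinded trial, settling the sets before database lock protects against choosing them by outcome. Here there is no blind to protect (Protocol 7.8). Investigator responses go into the eCRF at each scan (SAP 5.13.1), and interim ORR will already have been tabulated and individual responses listed (SAP 4.2). Unless response is deliberately withheld, the decision on who is excluded could be influenced by who responded.

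At stake is the value of the PPS as a check on the ITT result. ORR, PFS and OS are all repeated on it for Cohort A (SAP 5.13.1, 5.13.2.1 and 5.13.2.2).

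**Working it through.** The plan gives no figure to reproduce; SAP section 3 says that no formal sample size calculation was done. The check is a comparison of texts, followed by an illustration of scale.

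**Step 1: apply each rule to the same subject.**

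| Subject | SAP 5.3 / Protocol 11.7.1 | SAP 5.6 |
|---|---|---|
| No major deviation | In (the protocol also requires compliance) | In |
| Major deviation, judged serious for efficacy | Out | Out |
| Major deviation, not judged serious for efficacy | Out | In |

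The rules differ only in the third row. The documents do not say how many subjects would fall there; it could be none.

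**Step 2: is the difference declared?** No. Section 6, item 3, covers only the compliance clause. Its reasoning is that non-compliance would itself be a deviation. Under 5.3, however, a deviation excludes only if it is major, and under 5.6 only if it is also judged serious. The filter therefore weakens that reasoning too.

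**Step 3: could outcome reach the decision?**
- Open-label, non-randomised design: Protocol 7.8.
- Responses held in the eCRF: SAP 5.13.1.
- Interim ORR on the first 11 Cohort A subjects, with individual responses listed: SAP 4.2.
- Membership agreed when all data are available: SAP 5.3.
- A provision to mask response at the data review meeting: none found in either document.

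**Step 4: scale.** Inputs are 18 planned Cohort A subjects (SAP section 3) and, as an assumption, 8 responders. That is close to the 44% nivolumab response rate cited in the protocol synopsis. PPS ORR = responders remaining / subjects remaining.

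- No exclusions: 8/18 = 44.4% (exact 95% CI 21.5 to 69.2).
- Two non-responders excluded: 8/16 = 50.0% (24.7 to 75.3); 50.0 − 44.4 = +5.6 points.
- Two responders excluded: 6/16 = 37.5% (15.2 to 64.6); 37.5 − 44.4 = −6.9 points.
- One exclusion: 8/17 = 47.1% or 7/17 = 41.2%.
- Three exclusions: 8/15 = 53.3% or 5/15 = 33.3%.

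If Cohort A stayed at the 11 subjects recruited when enrolment was suspended (SAP section 4), and 5 of them responded (assumed), ORR without exclusions would be 5/11 = 45.5%. Two exclusions would give 5/9 = 55.6% or 3/9 = 33.3%.

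**The case against.** **The sections may be meant as one rule.** SAP 5.3 points to 5.6, so the 5.6 sentence could be explaining why a major deviation excludes. Most of the listed examples do bear on efficacy, and section 6 declares no filter, which suggests that none was intended. This is a fair account of intent. As written, though, 5.6 first sorts deviations into major and minor and then puts a condition on the major ones. If one rule was meant, the text should say so.

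**There are controls.** The Project Statistician co-approves, minutes are kept, and decisions precede database lock. Reasons for exclusion are listed (SAP 5.5), as is every deviation with its class and decision date (SAP 5.6). A reader could rebuild the set under either rule. All this stands. It makes the decisions traceable, but it does not keep outcome out of them.

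**Stronger readings that the documents do not support.**
- A reader might infer that the sponsor decides alone with responses on view. The co-approval contradicts the first part. The second is not stated anywhere: no text shows responses to the meeting, and none withholds them. The interim ORR also covers only the first 11 Cohort A subjects, not the planned 18.
- A reader might take 50.0% minus 37.5% as a 12.5-point swing from two decisions. That subtracts two opposite scenarios involving four different patients. Measured from the ITT value, two exclusions move ORR by +5.6 or −6.9 points, well inside the confidence interval.
- The illustration does not isolate the gap between 5.3 and 5.6. The same shifts could come from the major/minor call under 5.3 alone.

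**Conclusion.** The inconsistency is real and undeclared: a subject with a major deviation not judged serious for efficacy has two different PPS statuses. It is also correct that nothing in the documents prevents outcome from influencing membership. Whether it would do so is a possibility, not something the plan provides for.

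The consequence is small. ITT is the main analysis set and is unaffected. The PPS outputs cover Cohort A only, and all results are descriptive with no hypothesis tests (Protocol 11.3, SAP 5.14). It would go too far to conclude that the PPS is useless as a supportive set, since its exclusions are listed and can be reversed by a reader.

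The size, +5.6 or −6.9 points for two exclusions, rests on the assumed 8 responders in 18 and on both excluded subjects having the same response status. This is a low-cost improvement in wording and process, not a threat to the main result.

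**What to change.** 1. Use one exclusion rule in SAP 5.3 and 5.6. The default is the 5.3 and protocol rule, under which any major deviation excludes, with the impact sentence in 5.6 deleted. If an impact filter is wanted, define it by type of deviation and declare it in section 6.
2. Fix the list of excluding deviation types before the data review meeting. The interim reviews do not set the deadline, because interim efficacy uses ITT only (Protocol 11.1.6, SAP section 4).
3. Classify any deviation not on the list from a listing without response, progression or survival data. Criteria that depend on whether a scan or measurable lesion exists can be flagged by program without showing the result.

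The cost is a few lines of SAP text and one masked listing. The downsides are less room for case-by-case judgement and possibly a slightly smaller PPS, if a major deviation unrelated to efficacy excludes a subject.
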